
Alcohol Administration. Alcohol administration procedures are consistent with our previous work and NIAAA guidelines for the safe and ethical administration of alcohol in

experimental settings (Brown et al., 2014). Participants will complete two laboratory sessions in which they will be administered one of two beverages: placebo (0.00 g/dL target BrAC) or active alcohol (0.08 g/dL target BrAC). Session order will be counterbalanced across participants. For laboratory sessions in which a participant will be given the active dose, the quantity of medical/United States Pharmacopeia grade alcohol (100% or 95% ethanol) needed to achieve 0.08 g/dL (i.e., approximately 3-4 standard drinks) will be calculated using a modification of the Widmark formula. This formula utilizes age and weight measures for men and height and weight measures for women (Watson, et al., 1981; Widmark, 1932). For example, a 30-year old man who is 183 cm tall and weighs 75 kg would receive 55.3 ml of absolute ethanol, or ~.58 g/kg. In order to maintain the study's double blind, a researcher not involved in QST will be responsible for calculating alcohol doses and mixing drinks, and the dose calculation and mixing procedure confirmed by a second research assistant. Pre-calculated dose lookup tables indexing height and weight for women and age and weight for men will be used to avoid dosing errors. Alcohol will be mixed with cold sugar-free lemon-lime soda in a 1:3 ratio and split into two servings ([name], et al., 2014; Gilbertson, et al., 2009; Harrison et al., 2007). Placebo beverages will consist of only soda. Participants will consume both servings within 5 minutes. **Both active and placebo drinks will be misted with alcohol to enhance placebo effectiveness. A small amount of alcohol will be placed on the rim of the glass and floated on the surface of the beverage to further mask the study condition.** Participants will rinse their mouths thoroughly with water once their beverage has been consumed. No suggestion regarding the potential pain-relieving effects of alcohol will be provided before or after beverage administration to avoid influencing expectations. All study staff over the age of 21 designated as "Interacts or intervenes directly with study subjects" on the myIRB smart form will be trained by the PI how to use the lookup tables and mix beverages and may serve in this capacity depending on availability for a given laboratory session.

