Pain Induction Procedure. QST testing will occur in a private room within the Center for Pain Research and Behavioral Health using an approach developed by our research group (Brown et al., 2000). Pain induction will involve application of manual pressure to the insertion of the masseter muscle, 1 cm superior and anterior to the angle of the mandible. This location will be marked with ink to ensure a consistent stimulation site. For participants with TMD, pressure will be applied to the most affected (i.e., sensitive) side of the face, as determined during [name] examination. For control participants, the side of the face to be stimulated will be randomly determined. [name] will train the PI and all research assistants (RAs) to ensure consistent localization of this point across participants. Pressure will be increased over a 1s duration and maintained for 2s using a Wagner Force One pressure algometer (Wagner Instruments, Greenwich, CT). VAS pain intensity and unpleasantness ratings (anchored from "no pain at all"/"not at all unpleasant" to "most intense/unpleasant imaginable") will be collected. Ratings will be collected at 4, 5, and 6 foot pounds per square inch (fpsi). Pain ratings will also be collected 15 and 30 seconds after algometer removal to assess aftersensation. This procedure will be repeated three times, with pressures alternated in pseudorandom order. Mean pain ratings at each stimulation level will be used to calculate individualized slopes (representing discriminability between pressure stimuli) and intercepts (representing response bias) for each participant and treatment condition (i.e., active alcohol vs. placebo) (Brown et al., 2000). Pain threshold will also be assessed by increasing pressure on the masseter insertion at a rate of .5 fpsi/s. Participants will indicate when the sensation first becomes painful and provide a VAS rating of pain intensity at the threshold pressure. This procedure will also be repeated three times and threshold and pain intensity measures will be calculated as the mean of the three trials. Following each QST measure, participants will be provided with a 10 cm VAS assessing perceived relief from pain resulting from beverage consumption (anchored from "No relief at all" to "Most profound relief imaginable"). QST procedures will require approximately 15 minutes. During laboratory sessions, QST procedures will begin approximately 15 minutes after beverage consumption to allow for absorption of alcohol ([name] et al., 2014).

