
Data Analysis Strategy. Data will be analyzed using SPSS 24 (IBM Corp., Armonk, NY).

Aim 1. Determine the effect of chronic pain status on magnitude of alcohol analgesia and associated feelings of relief. To assess hypotheses and empirical questions related to Aim 1, chronic pain status will be included as an independent variable in repeated measures general linear models analyses (rmGLM; SPSS GLM procedure; repeated: dose), with QST measures, associated relief ratings, and SEAS measures as dependent variables. Demographic, personality/affective (i.e., BDI/STAI/IRQ/BFI), substance use-related (recent alcohol use/alcohol use disorder symptomatology), pain-related (TMD severity), and biological (i.e., approximated menstrual phase for female participants) variables will be included as covariates should any correlate significantly with magnitude of alcohol analgesia or relief ratings.

Aim 2. Determine the influence of typical alcohol use, and alcohol analgesia-related expectancies on magnitude of alcohol analgesia and associated feelings of relief. A combination of approaches will be used to address Aim 2. Simultaneous multiple regression of alcohol analgesia expectancy and typical alcohol consumption

(estimated in ounces of absolute ethanol consumed per day derived from the AUQ) on QST measures will be used to evaluate H4 and H5. As in Aim 1, rmGLM will be used to assess E2 and E3.

Power Analysis. Power analyses for the proposed work are based on effect sizes derived from our initial feasibility study (see attached grant application for details) and were performed assuming two-tailed hypothesis tests with alpha=.05. Effect sizes are reported as Cohen's d, Pearson's r, or R2 (Cohen, 1988). Analyses indicated N=50 would provide excellent (98%) power to detect analgesic effects of alcohol administration on QST measures (Cohen's d > .58) and correlations between VAS ratings of relief and alcohol analgesia (r = .64). Critically, this sample size will also provide 80% power to detect small-to-medium sized effects (d > .40; r > .37; R² > .14) for which prior estimates are not available (e.g., the effect of chronic pain status on alcohol analgesia and subject alcohol affects). *We will recruit a total of 60 qualified subjects over the course of the project to account for 10% anticipated participant dropout before completing all study visits.*

7. Possible Discomforts and Risks:

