QST Discomfort and Risks. QST, by definition, will induce pain in participants. However, risk of harm as a result of QST procedures is minimal for the following reasons: 1) the pain is transient in nature and generally subsides immediately after the procedure; 2) participants are instructed that they may stop any procedure at any time with no adverse consequences; and 3) although pain sensation may continue after pressure algometer removal (at discretion of the participant), this is not expected to last longer than 90 seconds. Furthermore, because pressure applied to the masseter will not exceed 8 foot pounds per square inch (fpsi) the risk of contusion is very slight. Should a participant suffer continued pain 24 hours after pressure algometry, an adverse event will be reported to the IRB.

Participant Confidentiality Risks. The investigative team places a high priority on protection of patient confidentiality and will use the following procedures to protect patients. Unique participant identifiers will be generated in order to collect protected health information (i.e., from questionnaires) for research purposes. Paper questionnaires and forms will be stored in a locked storage space, digital information will be stored in encrypted, password protected files on secure servers, and the data that links the participants to their unique identifiers will be stored in a separate location. When the study is completed and all raw data is entered electronically, participant identifiers will be destroyed. Despite these efforts, it is possible that participant confidentiality may be breached. If a breach occurs, it will be reported to NIH and the IRB and appropriate measures will be taken. These measures include but are not limited to informing affected participants of the breach and assisting with protective measures once the breach is detected.

Data and Safety Monitoring Plan

Because the proposed study does not comprise a clinical trial, a formal Data and Safety Monitoring Board has not been planned. The investigative team, including Drs. [name], [name], and [name], will meet quarterly to discuss data and safety monitoring issues. Any issues identified during these meetings will be handled in a manner consistent with the policies of the NIH and University of Florida.

8. Possible Benefits:

There are no potential benefits to participants in this study.

9. Conflict of Interest:

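### The Aim 1 repeated-measures GLM keeps only participants with both sessions; if dropout is related to pain, the group-by-dose (H3/E1) estimate can be biased, and a mixed model is safer

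*Combined protocol and SAP*

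**What the plan says.** Section 6, Data Analysis Strategy, Aim 1, specifies "repeated measures general linear models analyses (rmGLM; SPSS GLM procedure; repeated: dose"), with chronic pain status as the between-subjects variable and "with QST measures, associated relief ratings, and SEAS measures as dependent variables". Dose is the only repeated factor named.

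Under Alcohol Administration, "Participants will complete two laboratory sessions in which they will be administered one of two beverages", so each outcome has one placebo and one alcohol value per person. Under Pain Induction Procedure, "Ratings will be collected at 4, 5, and 6 foot pounds per square inch (fpsi"), with three repeats. Pressure then enters through summaries: "Mean pain ratings at each stimulation level will be used to calculate individualized slopes" and intercepts, for each participant and condition. For the separate threshold test, "threshold and pain intensity measures will be calculated as the mean of the three trials".

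The plan foresees incomplete data. Power Analysis recruits 60 to "account for 10% anticipated participant dropout before completing all study visits". Section 7, QST Discomfort and Risks, says "participants are instructed that they may stop any procedure at any time with no adverse consequences". Section 6 also discontinues people with a positive drug screen at a session, and section 7 allows withdrawal if the active dose is poorly tolerated. Nowhere does the document say how a missing session or rating is analysed.

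**The concern.** A repeated-measures GLM works on complete rows, so a participant with only a placebo or only an alcohol value leaves that analysis. This is a property of the procedure; the document does not state it. Over-recruitment protects the number of pairs but not the estimate.

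Some routes to an incomplete pair plausibly depend on pain or on response to the beverage. Someone who found the first session very painful may not return. If analgesia also varies with pain level, completers differ from everyone else in the quantity being estimated, and more so in the group that loses more people. H3 and E1 ask whether alcohol analgesia differs between TMD patients and controls, and in which direction, so a bias of unknown sign matters there.

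**Working it through.** **1. The plan's own figures.** Inputs (Power Analysis): N = 50, two-sided alpha .05, d = .58 and d = .40. For a paired t-test, the noncentrality is d√N.
- d = .58: .58 × √50 = 4.10, df = 49, power 0.980. The stated 98% reproduces.
- d = .40: .40 × √50 = 2.83, power 0.792. The stated 80% reproduces to rounding.
- Recruitment: 60 × 0.90 = 54 expected pairs, above the 50 powered. With 54 pairs, power is 0.987 and 0.823.

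So the number of pairs for the dose effect is adequate. The issue is which pairs remain.

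**2. What deletion costs in precision.** Assume all 6 dropouts give one session, 3 placebo and 3 alcohol, with between-session correlation ρ. The variance of the dose contrast is proportional to:
- complete pairs only: 2(1 − ρ)/54
- likelihood analysis: 2 / [54/(1 − ρ) + 3]

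The relative gain is 3(1 − ρ)/54.
- ρ = .9: 3 × 0.1/54 = 0.6%, effective N 54.3
- ρ = .3: 3 × 0.7/54 = 3.9%, effective N 56.1

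Uneven splits of the six give between about 0.5% and 4%. Normal-approximation power for the dose effect at d = .40 moves from 83.6% to between 83.8% and 85.0%. The precision argument is weak.

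**3. What deletion can do to the estimate.** The complete-pair bias is the shift in mean analgesia caused by selecting completers in the TMD group, minus the same shift in controls. The document gives no dropout pattern, so what follows rests on assumptions.

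*Proportional analgesia.* Assume alcohol removes 20% of pain and TMD ratings are 15 VAS points higher. The true group-by-dose difference is 0.20 × 15 = 3.0 points. Let 10% drop out after session 1, driven by first-session pain.

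| Analysis | Estimate (true 3.0) | Shortfall |
|---|---|---|
| Complete pairs | 2.4 to 2.8 | 0.6/3.0 = 20% to 0.2/3.0 = 7% |
| Maximum likelihood, all sessions | 2.9 to 3.0 | 0.1/3.0 = 3% to 0% |

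To see the mechanism: if selection acts only through pain level, an estimate of 2.4 means that the gap between groups among completers has fallen from 15 to 2.4/0.20 = 12 points.

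*Other relations between pain and analgesia.* This is a harsher case: TMD sensitivity 0.8 SD higher, 20% of TMD pairs and 5% to 9% of control pairs lost, true contrast +0.40 or −0.40. Ratio of completer estimate to truth when loss depends on sensitivity alone:

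| Correlation of sensitivity with analgesia | TMD analgesia larger | TMD analgesia smaller |
|---|---|---|
| −0.5 | 1.25 | 0.75 |
| 0 | 1.00 | 1.00 |
| +0.5 | 0.75 | 1.25 |

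Across all loss mechanisms tried, the ratio ran from 0.64 to 1.25. With equal random loss it was 1.00.

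**4. A missing pressure level.** Pressure is not a repeated factor, so a person who declines 6 fpsi can still have a line fitted through 4 and 5 fpsi. With that two-level fit and the same paired analysis, simulated estimates were 3.03 to 3.12 against a true 3.0, which is close to unbiased. The cost is noise, in units of residual variance:
- Slope: the sum of squares of pressure falls from 2 to 0.5, so the variance rises from 1/2 to 1/0.5 = 2 (4-fold).
- Intercept: from 1/3 + 5²/2 = 12.8 to 1/2 + 4.5²/0.5 = 41 (3.2-fold).

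The GLM gives such a summary the same weight as a full one.

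**The case against.** The strongest reply is that this is only an unwritten missing-data rule. One sentence on computing slope and intercept from the available levels would suffice, 54 expected pairs exceed the 50 powered, and single sessions add almost no information.

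Much of that stands. A reader might infer that declining the strongest pressure removes a participant from Aim 1. The document does not support this: dose is the only repeated factor, slope and intercept can be fitted from two levels, a level's mean survives if one repeat is refused, and neither threshold nor SEAS uses the 6 fpsi rating. Deletion would follow only if the summary were set missing without all three levels, or if pressure were entered as a second repeated factor. The plan says neither.

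A reader might also infer that the H3 estimate must shrink. Section 5 leaves the direction of the group difference open, and the second table shows that the estimate can fall, rise or stay put. Nor does the plan predict who will stop or how often; the permission to stop is a safeguard. Some of the 10% may leave after screening, which already includes pressure algometry, and no model recovers them.

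The reply does not deal with the missing session. A rule for fitting lines cannot help someone who has no second session. The named procedure must delete that person, while a likelihood analysis need not.

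**Conclusion.** The concern holds for missing sessions. The named Aim 1 method discards incomplete pairs that the plan itself expects, and the H3/E1 estimate is then exposed to bias if loss depends on observed pain and analgesia is related to pain level. The size is 7% to 20% towards zero under 10% dropout driven by first-session pain, 20% proportional analgesia and higher TMD ratings. The bias may be in either direction under other relations, and there is none if loss is unrelated to pain or response. All these conditions are assumptions, because the document gives no rates or patterns.

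The stronger readings, that a missing pressure level deletes a participant, that the H3 estimate certainly shrinks, or that much information is thrown away, are not supported. The change is worth making because it is cheap and protects the comparison of most interest. The problem does not invalidate the design.

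**What to change.** In section 6, Data Analysis Strategy, Aim 1:

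- Make a linear mixed model (SPSS MIXED, REML) the primary analysis and keep single-session participants. Fixed effects: dose, chronic pain status and dose-by-status (the H3 test), with session order as a covariate. Participant is the random unit. Let the placebo and alcohol variances differ, because proportional analgesia makes them unequal and an equal-variance model would then correct only part of the bias.
- For the QST ratings, fit the individual ratings with pressure centred at 5 fpsi and its interactions with dose and status. Include random participant intercept, dose and pressure effects, so that repeated ratings within a session are not treated as independent. Centring makes dose-by-status the contrast at the middle pressure; uncentred, it would refer to 0 fpsi, outside the tested range. The dose-by-pressure terms carry the planned slope outcome, and incomplete pressure sets are used with proper weight.
- For threshold, relief and SEAS, use the same model without pressure.
- Keep the complete-pair repeated-measures GLM as a sensitivity analysis. State for it how slope and intercept are computed when a level is missing.
- Report by group and session how many participants lack a session or a pressure level, and why.

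Cost: revised wording and slightly more programming in the same software, with no new data. The mixed model relies on data missing at random given the observed ratings. That is an assumption, but a weaker one than complete-pair analysis needs.

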Aim 2. Determine the influence of typical alcohol use and expectation of pain relief with alcohol use on magnitude of alcohol analgesia and associated feelings of relief. Studies of alcohol analgesia in healthy adults have indicated that individual patterns of typical alcohol use, motivation to drink, and personality factors may modulate alcohol analgesia, suggesting a critical role of conditioning and expectancies (Brown and Cutter, 1977; Cutter et al., 1979; Ralevski et al., 2010). However, this question has never been directly examined, either in healthy adults or those with chronic pain. **H4.** We predict individuals with stronger positive expectancies regarding alcohol analgesia will have significantly stronger analgesic responses to alcohol administration. **H5.** Based on previous research, we predict that individuals who endorse greater and more frequent alcohol consumption will experience a greater analgesic effect of alcohol, independent of the effect of expectancies. Finally, we ask as **E2.** whether chronic pain status will be associated with stronger expectancies of pain relief following alcohol consumption and **E3.** greater ratings of pain relief during pressure algometry after drinking.

6. Research Plan:

General Approach. For this study of current non-problem drinkers, we propose a repeated-measures, double blind placebo-controlled factorial design with chronic pain status (TMD vs. healthy control) as a between-subjects factor and alcohol administration (Alcohol Dose: placebo, 0.08 g/dL) as a within-subjects factor. The study will include both men and women. Study procedures will occur at the Center for Pain Research and Behavioral Health of the University of Florida under supervision of the PI (JB).

Methods

Participants. Individuals seeking care for temporomandibular joint and muscle disorder (TMD) (n=25) will be recruited for the study via flyers, word of mouth, internet/local radio advertisements, and [name] orthodontic clinic. A sample of healthy social drinkers without TMD (HC) will also be recruited as a comparison group (n=25). Individuals aged 21-45 years will be recruited to avoid any vulnerability to acute neurobehavioral effects of alcohol associated with older age (e.g., [name] et al., 2016a). Because TMD is more prevalent in women than men (~2:1; Campbell et al., 2017), we anticipate the final sample will consist of approximately 2/3 women.

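### No QST measure is named as the test of H1 or H3, so a significant result on any one of about five to eight unranked measures could be taken as support

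*Combined protocol and SAP*

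**What the plan says.** Section 5, Aim 1, states H1 and H3 as predictions and keeps them apart from the open empirical questions (E1 to E3). H1 expects a significant fall in pain sensitivity on alcohol compared with placebo, in TMD patients and in controls. H3 expects chronic pain status to change the size of the effect, and E1 leaves the direction open. Neither names a measure. Perceived relief has its own hypothesis, H2.

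Section 6, Pain Induction Procedure, describes the measures. Intensity and unpleasantness are rated at three pressures, and "Mean pain ratings at each stimulation level will be used to calculate individualized slopes", together with intercepts. Ratings are repeated 15 and 30 seconds after the algometer is removed. Pain threshold and the intensity rating at threshold are each averaged over three trials.

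Section 6, Data Analysis Strategy, Aim 1, puts all of this into repeated-measures general linear models "with QST measures, associated relief ratings, and SEAS measures as dependent variables". It does not rank the measures, combine them, adjust for their number, or say how many must agree. It also does not say whether they are modelled separately or jointly. The only error level is in the Power Analysis paragraph, where the calculations were made "assuming two-tailed hypothesis tests with alpha=.05".

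**The concern.** A prediction of reduced pain sensitivity can be tested by threshold, by an intercept, by a slope, by aftersensation or by intensity at threshold. The plan does not choose among them and gives no rule for mixed results. Followed as written, one significant measure among several could be reported as alcohol analgesia, or as a difference between TMD patients and controls.

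H3 is the more exposed, because a difference in either direction on any measure would fit it.

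The abstract also says the study should supply effect sizes for later proposals. An effect size taken from whichever measure reached significance will tend to be too large, so the choice matters for that purpose as well.

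Covariates enter the model if they correlate significantly with the analgesic effect or with relief. With no fixed outcome, the model itself can therefore differ from measure to measure. The figures below do not include that extra flexibility.

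**Working it through.** **The plan's own power figure.** Inputs from Power Analysis: N = 50, d = .58, two-sided .05. For a paired test the noncentrality is .58 × √50 = 4.10, with 49 degrees of freedom and critical t = 2.01. Noncentral t gives 98.0%, matching the stated 98%. That figure therefore belongs to one test at the full .05.

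**Number of QST measures (k).** The documents give no count, so this is read from Pain Induction Procedure:
- Slope and intercept: 2 if fitted to one rating scale, 4 if fitted to both. The text does not say which.
- Aftersensation: 2 (15 s and 30 s), or 1 if treated as a single measure.
- Threshold and intensity at threshold: 2.

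The low reading is 2 + 1 + 2 = 5. The fuller reading is 4 + 2 + 2 = 8. (Scoring aftersensation on both scales would give 10; this is not used below.)

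**Chance of at least one false positive.** Assume no true effect on any measure, each tested at two-sided .05, and any one significant result counted as support.

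- H3, either direction counts. Independent measures: 1 − .95^k. For k = 8, 1 − .6634 = 33.7%. For k = 5, 1 − .7738 = 22.6%.
- H1, only the predicted tail counts (.025 per measure). Independent measures: 1 − .975^k. For k = 8, 18.3%. For k = 5, 11.9%.

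The measures come from the same face and session, so they will be correlated. The documents give no correlations; a common value ρ is assumed. With c = 1.96, z standard normal with density φ, and Φ its distribution function:
- H3: 1 − ∫ φ(z) [Φ((c − √ρ z)/√(1−ρ)) − Φ((−c − √ρ z)/√(1−ρ))]^k dz
- H1: 1 − ∫ φ(z) [Φ((c − √ρ z)/√(1−ρ))]^k dz

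| Assumed ρ | H3, k = 8 | H3, k = 5 | H1, k = 8 | H1, k = 5 |
|---|---|---|---|---|
| 0 | 33.7% | 22.6% | 18.3% | 11.9% |
| .5 | 25.0% | 18.3% | 12.5% | 9.2% |
| .7 | 19.1% | 14.8% | 9.5% | 7.4% |
| One test only | 5% | 5% | 2.5% | 2.5% |

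Simulated t tests with k = 8 (paired, N = 50; and 25 versus 25 for the interaction) agree for the two-sided rates: 33 to 34%, 25% and 20% at ρ = 0, .5 and .7. At ρ = .9 the H3 rate with eight measures is still about 12%.

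**What the remedies do to power.** One named outcome keeps .05 and 98.0% at d = .58. Bonferroni over eight instead (.05/8 = .00625) gives 88.7% at the same d.

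**The case against.** A reader might add up every dependent variable listed for Aim 1. Eight QST summaries, one or two relief ratings and four SEAS scores make 13 or 14, or up to 16 if aftersensation is scored on both scales. With 13 to 15 independent tests the chance of a false positive is 49 to 54%. The documents do not support that for H1 or H3. Relief is the subject of H2, and SEAS belongs to no numbered hypothesis; it is collected to see how subjective effects contribute to analgesia. A significant SEAS score could not be claimed as support for H1 or H3.

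Nor do the H3 rates carry over to H1. H1 predicts a reduction, so a significant increase in sensitivity would not support it, and its rate is roughly half. It would be lower still if H1 required significance in both groups on the same measure, but the plan sets no such rule.

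Eight is also not a minimum. The text does not say that slopes and intercepts are fitted to both scales, and it describes slope as discriminability and intercept as response bias, so not every summary is plainly a measure of pain sensitivity.

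Finally, the protocol aims at feasibility and effect-size data, and its Data and Safety Monitoring Plan says the study is not a clinical trial. That softens the consequence. It does not remove it, because H1 and H3 are worded as predictions, separate from the questions left open, and H1 is worded in terms of significance.

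**Conclusion.** The concern stands in a limited form: the plan has no rule for deciding H1 or H3 among about five to eight QST measures. If one significant measure is enough, the chance of false support is about 19 to 34% for H3 with eight measures and 15 to 23% with five. For H1 it is about 10 to 18% and 7 to 12%. Every figure is well above the level for a single test (5% for H3, 2.5% for H1).

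These sizes rest on four assumptions:
- The count is read from the described procedure.
- .05 is used for each measure, inferred because no other level or adjustment is given.
- All measures share a common correlation between 0 and .7.
- For H1, every measure is scored so that analgesia points the same way. The plan does not say which direction of slope or of intensity at threshold counts as analgesia.

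The design itself is not in question; the decision rule is what is missing.

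**What to change.** Before analysis, add one paragraph to Data Analysis Strategy:

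- Name one QST outcome as primary for H1 (dose effect) and H3 (dose-by-group interaction), each at two-sided .05. A measure that Pain Induction Procedure already defines would do, such as threshold or the intensity intercept. Mean intensity over the three pressures is an alternative if the sponsor prefers it. State which direction counts as analgesia.
- Name the relief VAS as the outcome for H2 at two-sided .05. It is collected after each QST measure, so say how the ratings are combined.
- Treat the remaining QST measures as secondary with Holm adjustment, and list them, including which rating scales are used for slopes, intercepts and aftersensation.
- Label SEAS exploratory.
- Say whether H1 is judged on all participants or separately in each group. The stated 98% is for all 50; with 25 in a group, the same paired test at d = .58 has 79.5%.

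No new data, visits or participants are needed. The cost is some loss of power for the secondary QST measures. The stated 98% at d = .58 is kept for the primary alcohol effect. Naming the outcome neither raises nor lowers the power of the group comparison in H3.
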